For safety purposes, use of the LFMS device follows standard MRI procedures. The LFMS device is assessed by the McLean Hospital Biomedical Engineering department annually to ensure the device operates within safe parameters.

e. Withdrawal Criteria:

Participation in this research study is voluntary. Subjects will be informed that they may withdraw from this study at any time. Subjects also will be informed that study staff may terminate participation at any time if they feel that it is in the best interest of the subject or study.

Objective criteria for removing a subject from the study include: if they become no longer eligible for the study between screening and treatment per inclusion/exclusion criteria (e.g. drug use or pregnancy), if they have dangerous or active suicidal ideation at any time during the study (as determined by C-SSRS and suicide related questions on the MADRS and the opinion of a study clinician), or if their CGI-I score, determined as part of the Safety Measures, shows a change of ≥ 8 , or if any intolerable discomfort from the study procedures occurs.

f. Source of subjects and recruitment methods

Study subjects will be recruited via clinician referrals from the Geriatric Psychiatry Mood and Anxiety Disorders Outpatient Clinic (GPMADOC) and the SAGE Program, located in South Belknap. Clinicians associated with these

Low Field Magnetic Stimulation: Initial Trial in Geriatric Bipolar Depression

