At the phone screen and on site screening, potential subjects are informed that we do not ask them to discontinue their medications or treatments. However, we ask that they do not make changes to their medications or therapy prior to or during the experimental study period. Stable medication is not a confound. Subjects are also told that if their clinician believes it is in their best interest to make this change, they should do so. They will be asked to inform us if this is the case. We will not ask the subject to withdraw from the study, but their data will be excluded from analyses. If a subject withdraws from the study due to a change in medication, pregnancy or any other reason not related to the actual LFMS procedures and would like to return to the study in the future, they will be allowed to re-enroll. However, they must go through a 2 month washout period. The subject will be partially rescreened to confirm mood state and inclusion/exclusion criteria prior to their first treatment visit.

j. Study visits and parameters to be measured (e.g., laboratory tests, x-rays, and other testing)

Measures

Screening measures

- M.I.N.I International Neuro-Psychiatric Interview (MINI)
- Cumulative Illness Rating Scale – Geriatrics (CIRS-G)

Low Field Magnetic Stimulation: Initial Trial in Geriatric Bipolar Depression

- Montgomery Asberg Depression Rating Scale (MADRS)
- Mini Mental State Exam (MMSE)
- Hamilton Anxiety Rating Scale (HARS)
- Positive and Negative Affect Schedule (PANAS)
- LFMS Medical Screening Form
- LFMS Medications Form
- Clinical Global Impressions – Baseline (CGI-B)

Safety Measures

- Columbia Suicide Severity Rating Scale (C-SSRS)
- Clinical Global Impressions – Improvement Scale (CGI-I)

Long-term measures

- Montgomery-Åsberg Depression Rating Scale (MADRS)
- Hamilton Anxiety Rating Scale (HARS)
- Repeatable Battery for the Assessment of Neuropsychological Status (RBANS)
- Young Mania Rating Scale (YMRS)

Short-term measures

- Positive and Negative Affect Schedule (PANAS)

Screening (Visit 1) Procedures

A study staff member will obtain informed consent (see consent procedures above IV.b.). If informed consent is obtained, then the screening procedures will proceed.

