The Safety Measures will be administered. As part of these, the C-SSRS will be used as a suicidality risk assessment and any positive response to items 4 or 5 will prompt the use of the Suicidality SOP (see ‘Suicidality Procedures’ above). The second part of the Safety Measures is the CGI-I, which will be used to ensure safe continuation of the study; a score of 6 or more will prompt a consultation with the study physician and potential withdrawal from the study (see “Withdrawal Criteria” above). Medication and/or treatment changes will be asked about and noted. Changes in treatment will not prompt withdrawal but will indicate that data will be excluded from analysis (see “Medication and Therapy Change Procedures” above). A brief progress note will be recorded. The Short- and Long-Term mood scales will be

Low Field Magnetic Stimulation: Initial Trial in Geriatric Bipolar Depression

administered, and LFMS procedures will begin immediately after these mood ratings are completed. HARS and MADRS Long-Term mood scales will only be administered on Visits 3, 5, and 7.

Randomization occurs automatically when the subject number is entered on the LFMS Device during the first treatment visit.

For LFMS procedures, the subject will lie down on the patient table with his/her head positioned inside the device cylinder, and the operator will start the LFMS device. The device has been designed so that the cylinder does not extend below the eyes in order to reduce claustrophobia. Subjects will be instructed to remain silent during the treatment, except in cases of discomfort, desire to discontinue treatment, or similar situations related to subject safety and study participation. Subjects will be given one 20 minute exposure to either the LFMS or sham electromagnetic field treatment. Subjects will be told they may receive either the active treatment or a sham, inactive treatment.

After treatment, the Short-Term Measures will be completed again to obtain post-treatment scores. Subjects will also be asked about possible side effects or sensations. After the treatment and mood ratings, subjects may leave immediately or rest in the Imaging Center waiting area until they are ready to leave or return to the GPMADOC and the SAGE Program, located in South Belknap.

Follow-up Visit (Visit 8)

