Due to the nature of affective disorders, it is possible that a subject may develop or experience an increase in suicidal ideation during their participation in the study. If it is determined that a subject has developed increased suicidal thinking, either through increased scores on the or through conversation with clinical study staff, a study physician and the subject's clinician will be called immediately.

e. Drug side effects and toxicities

N/A

f. Device complications/malfunctions

Risks Related to LFMS Device

LFMS technology does not use ionizing radiation. Instead, it uses electric field pulses that may stimulate the brain. There are no known hazards or risks associated with this technique. The LFMS device, unlike an MR scanner, has no permanent magnet and thus has no magnetic field when not in active operation. During treatment there is a small, low frequency magnetic field near the device. This field is less than 5 Gauss when further than 1.5 feet from the device. We plan to be conservative and follow the 5 Gauss guidelines for MRI sites and place a magnetic area sign in the doorway during treatment sessions, to warn anyone who may enter the room during the 20 minute treatment. Outside of the treatment time, there are no fields and thus no safety issues.

Persons with pacemakers, neurostimulators, or metal in head or neck will not be enrolled or allowed in the room during device operation.

Low Field Magnetic Stimulation: Initial Trial in Geriatric Bipolar Depression

There is a red button on the device that can be manually pushed in the event of a hardware failure or an emergency. This mechanically disconnects the coil from the power source and dumps the energy stored in the coil safely to a heat dissipative resistor. If the subject asks to terminate the experiment or experiences a medical emergency, there is a “stop” button on the interface that can be clicked with the computer mouse, and this will stop waveform execution.

Risks Related to Pregnancy

There are no known risks for pregnancy associated with this type of electromagnetic field exposure. However, in order to ensure subject safety, women who are pregnant, as confirmed by pregnancy test, will be excluded from this study.

Radiation Risks (statement provided by Radiation Safety Committee)

N/A

VIII. POTENTIAL BENEFITS

b. Potential benefits to participating individuals and/or to society

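### Phase 2 takes subjects stopped for ideation, worsening or discomfort out of the study rather than off LFMS, so those removed before Visit 8 have no planned one-week MADRS or HARS

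*Combined protocol and SAP*

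**What the plan says.** Phase 2, III.e opens its list with "Objective criteria for removing a subject from the study include". After a pre-treatment loss of eligibility, it names three events that can arise once treatment has begun: ideation ("if they have dangerous or active suicidal ideation at any time during the study"), a CGI-I change of 8 or more, and discomfort ("or if any intolerable discomfort from the study procedures occurs"). Phase 1, III.b has the same rule.

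There are two further routes out. Under Phase 2, V, LFMS (Visits 3-7) Procedures, a CGI-I score of 6 or more leads to a physician consultation and possibly to withdrawal from the study. III.e and IX.d also let study staff or the principal investigator end participation at their discretion.

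On ratings, Phase 2, V states "HARS and MADRS Long-Term mood scales will only be administered on Visits 3, 5, and 7", and these are taken before that day's LFMS. The one-week rating is Visit 8, on the Monday after the treatment week, followed by two weekly calls. VI.d makes the one-week change in MADRS and HARS the primary long-term measures.

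A separate rule covers medication or therapy changes (V.i): "We will not ask the subject to withdraw from the study, but their data will be excluded from analyses". The treatment-visit and Visit 8 sections repeat it: "Changes in treatment will not prompt withdrawal but will indicate that data will be excluded from analysis".

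**The concern.** Stopping the device and leaving the study are different events, and the text treats them as one. The treatment-visit section recognises that a subject may want to stop during a session (silence is required "except in cases of discomfort, desire to discontinue treatment, or similar situations related to subject safety and study participation"), but no section says what is rated afterwards. Visit 8 and the calls are described only as following the treatment set.

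The subjects affected are selected for ideation, global worsening or discomfort, and the first two are close to what MADRS measures. Their one-week scores are missing for reasons plausibly related to outcome. That can distort the one-week active-sham comparison, from which VI.f expects a first effect-size estimate. Later research C-SSRS, CGI-I, YMRS and adverse-event checks lapse for the same people, although Aim 1 includes safety.

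The medication-change rule could undo a partial repair. If a stopped subject's treatment is then changed, any one-week score collected would still be dropped from analysis.

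**Working it through.** The plan gives no figure to reproduce: VI.f states that no power analysis was done, and no removal rate is given. The check is a reading of the rules plus counts from the Phase 2 visit table.

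**Is there a provision elsewhere?** The two nearest do not fill the gap. One missed treatment visit is tolerated (V, Study Overview and LFMS Procedures), but that concerns scheduling. Subjects with a medication change stay in the study (V.i), but that rule covers only such changes and excludes their data. No section describes an early-termination assessment or a rule for missing one-week scores.

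**Inputs.** C-SSRS, CGI-I, YMRS and the adverse-event check are planned at Visits 3 to 8 and at both calls. MADRS and HARS are planned at Visits 3, 5, 7 and 8 and at both calls. The Visit 3 rating precedes the first exposure.

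**Counts.** Later contacts after removal at Visit v = (8 − v) + 2. Later MADRS/HARS = those of Visits 5, 7 and 8 that come after v, plus 2. Post-LFMS MADRS/HARS in hand = those of Visits 5 and 7 up to and including v. This last count is a maximum, because it assumes that the rating was done on the day of removal.

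| Removed at | Later safety contacts not provided for | Later MADRS/HARS not provided for | Post-LFMS MADRS/HARS in hand, at most | One-week value in hand |
|---|---|---|---|---|
| Visit 3 | 5 + 2 = 7 | 3 + 2 = 5 | 0 | 0 |
| Visit 4 | 4 + 2 = 6 | 3 + 2 = 5 | 0 | 0 |
| Visit 5 | 3 + 2 = 5 | 2 + 2 = 4 | 1 | 0 |
| Visit 6 | 2 + 2 = 4 | 2 + 2 = 4 | 1 | 0 |
| Visit 7 | 1 + 2 = 3 | 1 + 2 = 3 | 2 | 0 |

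The Visit 3 row applies only to events during or after the first session. Ideation or worsening found on that day's ratings is pre-exposure.

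**What follow-up could recover.** Visit 8 plus two calls gives at most 3 contacts and 3 MADRS/HARS ratings per subject. For removal at Visits 3 to 7 this leaves at least 7 − 3, 6 − 3, 5 − 3, 4 − 3, 3 − 3 = 4, 3, 2, 1, 0 contacts uncollected. For MADRS/HARS it leaves at least 5 − 3, 5 − 3, 4 − 3, 4 − 3, 3 − 3 = 2, 2, 1, 1, 0.

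**Illustration on assumed values only.** If r of n subjects in one arm are removed and are g SD worse at one week than those retained, the retained mean differs from the full-arm mean by (r/n) × g. Assume n = 16 (half the 32-completer target), r from 1 to 4 and g from 0.5 to 1.5. The shift runs from (1/16) × 0.5 = 0.03 SD to (4/16) × 1.5 = 0.38 SD. The standard error of the arm difference is √(2/16) = 0.35 SD. None of n, r or g comes from the plan, so this range is not an estimate of bias. It shows only that the effect could be negligible or material.

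**The case against.** The case for leaving the rule alone has substance. The main endpoint is tolerability of five daily treatments (VI.e), and stopping for discomfort is itself information on that. The study is called exploratory, is sized on completers (III), and Hypothesis 1 concerns mood after five days of LFMS. Dangerous or active ideation is excluded at entry, treatment lasts one week, and the protocol reports no physical sensation and no known hazards, so removals may be few. Removal is also partly discretionary: ideation depends in part on a clinician's opinion, and the CGI-I score of 6 leads only to potential withdrawal. All of this limits the weight of the point. It does not supply the missing one-week rating.

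Some stronger readings are tempting, but the documents do not support them:

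- *Removed subjects are abandoned.* VII.d says that for increased suicidal thinking a study physician is called and the subject's own "clinician will be called immediately". Adverse-event reporting continues, and nothing forbids later contact. The consent pages and the Suicidality SOP are not in the text reviewed.
- *Removed subjects have no mood data.* Baseline, PANAS up to removal and any earlier MADRS/HARS remain.
- *The medication-change rule will exclude them anyway.* A treatment change after stopping is an inference. The call in VII.d supports it only for increased suicidal thinking. For CGI-I worsening the text provides a study-physician consultation only.
- *Half the sample is expected to be lost.* Enrolling up to 64 for 32 completers allows 1 − 32/64 = 50% non-completion, but the plan does not separate screen failures from removals after randomisation.

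**Conclusion.** The point holds as a statement about the protocol text. If the rule is followed as written, anyone removed between the first session and Visit 8 has no planned one-week MADRS/HARS, at most 0 to 2 post-LFMS ratings depending on the visit, and 3 to 7 later safety contacts with no provision. The loss falls on subjects whose state is close to the outcome.

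A reader might infer that the one-week comparison is biased towards active LFMS. The documents do not support that: they give no removal rate by arm and no outcome data for removed subjects, so frequency, size and direction are all unknown. The tolerability endpoint, the triggering event and acute care are unaffected. This is an improvement the sponsor should make because it is cheap and because the primary long-term measures depend on it. It is not a flaw that invalidates the study.

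**What to change.** Keep the stopping criteria, and leave the pre-treatment eligibility criterion as it is. In Phase 2, III.e, for events from the first LFMS session onward, make ideation, CGI-I change and intolerable discomfort grounds for discontinuing LFMS rather than for leaving the study. Treat the CGI-I score of 6 or more and discretionary terminations by staff or the principal investigator in the same way.

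With the subject's agreement and a study clinician's approval, collect MADRS, HARS, C-SSRS, CGI-I, YMRS and the adverse-event check at the original Visit 8 date and at both calls, by phone if needed. Before un-blinding, record the reason for stopping and any treatment change with its date.

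Report these subjects by randomised arm in the safety results and in an all-randomised one-week mood analysis. Show beside it an analysis that excludes them, which stays closer to Hypothesis 1. State in V.i, and where the rule is repeated, that the medication-change exclusion does not remove their data from the all-randomised analysis.

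The cost is protocol and consent wording, a few extra contacts, and $30 for each extra Visit 8 attended (III.f; phone follow-ups are unpaid). Visit 8, the calls and the forms already exist. Some stopped subjects will decline and remain missing, and one-week scores may partly reflect rescue treatment, which is why the dated treatment record and the second analysis are needed.

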Clinical Global Impressions-Improvement Scale (CGI-I)			X	X	X	X	X	X	X	X
Clinical Global Impressions-Baseline		X								
Adverse Events Check-in		X	X	X	X	X	X	X	X	X

*Administered twice per visit, immediately before and immediately after LFMS treatment.

Safety Procedures

h. Suicidality Procedures

Suicidal ideation (SI) is not uncommon in people suffering from GBD. Suicidality will be assessed throughout the study during the screening visit, treatment visits and follow-up visits. Using the C-SSRS. The GPMADOC suicidality SOP will be prompted by over threshold responses for certain items on mood rating scales or by spontaneous report of suicidal ideation at any time. Specifically,

- The use of the GPMADOC Suicidality SOP will be triggered by spontaneous report of suicidal ideation or by over-threshold responses to specific items on mood ratings.
- The Suicidality SOP instructs the use of the C-SSRS and uses the responses to questions 4 and 5 as a threshold for physician involvement. If the responses to these two questions are “yes” then the study physician will be contacted for in-person assessment or for phone call-back assessment as appropriate. The C-SSRS will be completed while awaiting the physician.
- The following mood rating items and thresholds trigger use of the Suicidality SOP: C-SSRS, “yes” to questions 4 and 5; MINI, “yes” on items B7, B9 or B10; MADRS, 4 or 6 on item 10.

We note that the CGI is used for withdrawal criteria, but this scale is not used for suicidality assessment, but rather to ensure safe continuation of the study.

i. Medication or Therapy Changes

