The Monday following the set of 5 treatments (visits 3-7), subjects will meet with the study staff for a non-treatment follow-up visit. This visit will last up to 1 hour. During this visit, the Safety measures will be administered. As part of these, the C-SSRS will be used as a suicidality risk assessment and any positive response to items 4 or 5 will prompt the use of the Suicidality SOP (see ‘Suicidality Procedures’ above). Medication and/or treatment changes will be asked about and noted. Changes in treatment will not prompt withdrawal but will indicate that data will be excluded from analysis (see “Medication and Therapy Change Procedures” above).

The Long-term measures will be completed, as well as the PANAS. Subjects will be asked if they have experienced any change in their mood or noticed any effects. In addition, subjects will be asked whether they think they received active or sham LFMS.

Follow-up Phone Calls

In order to determine whether any effects are still felt after treatment stops, study staff will make one follow-up phone call each week on Monday for the 2 weeks after the Follow-up Visit. Short- and Long-Term Measures will be administered, and study staff will ask whether the subject has experienced any adverse side-effects. Safety Measures including the C-SSRS and the CGI-I will be administered, and a positive response to question 4 or 5 on the C-SSRS will trigger the Suicidality SOP.

k. Drugs to be used (dose, method, schedule of administration, dose modifications, toxicities), include Toxicity Grading Scale (if applicable)

N/A

l. Devices to be used

The LFMS Device is an electromagnetic coil situated on a cylinder with an inside diameter of 13.2 inches. It produces weak electromagnetic fields at a frequency of about 1000Hz; the magnetic fields are less than 30 Gauss and the electric fields are up to 1.43 V/m. A fully detailed description of the electromagnetic field distribution and waveform has been presented in the IDE submission to the FDA (and determined to be a non-significant risk device).

m. Procedures/surgical interventions, etc.

N/A

n. Data to be collected and when the data is to be collected

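### The objective CGI-I removal criterion (change of 8 or more) names no reference rating and, on an assumed 1-7 form, can never be met

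*Combined protocol and SAP*

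**What the plan says.** The Withdrawal Criteria (Phase 1, III.b; Phase 2, III.e) open with a general discretion clause: "study staff may terminate participation at any time if they feel that it is in the best interest of the subject or study". They then list objective criteria for removal. One of these is that the subject's "CGI-I score, determined as part of the Safety Measures, shows a change of ≥ 8". The wording is the same in both phases.

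The treatment-visit procedures (Phase 1, LFMS Visits 2-4 and 6-8; Phase 2, LFMS Visits 3-7) use a different measure, the score itself: "a score of 6 or more will prompt a consultation with the study physician and potential withdrawal from the study". They refer the reader back to the Withdrawal Criteria, where no score of 6 appears. The check comes before exposure. In the Phase 2 text, "LFMS procedures will begin immediately after these mood ratings are completed", and Phase 1 has an equivalent sentence.

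The Suicidality Procedures state the purpose of the scale: "We note that the CGI is used for withdrawal criteria", and they add that it serves safe continuation rather than suicidality assessment.

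A baseline CGI (CGI-B) is collected once. The schedule tables place it at Visit 1 in Phase 1 and at Visit 2 in Phase 2, although the Phase 2 text also lists it among the screening measures. No text links it to the removal criterion.

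At follow-up the CGI-I is scheduled, but the only action restated there is the one for the C-SSRS. For the Phase 2 calls: "Safety Measures including the C-SSRS and the CGI-I will be administered, and a positive response to question 4 or 5 on the C-SSRS" leads to the suicidality procedure. No CGI-I action is given.

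**The concern.** A criterion labelled objective should give the same answer whoever applies it. This one does not say what the change is measured from, or whether it means worsening only. Its size also looks too large for a short rating scale. If the form has fewer than nine levels, the criterion is on paper but cannot operate.

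The other listed removal criteria are loss of eligibility between screening and treatment, suicidal ideation, and intolerable discomfort from procedures. The CGI-I clause is therefore the only listed objective criterion that could catch general, non-suicidal worsening. What is at stake is whether the plan has a working rule of that kind, and whether a poor CGI-I rating at a follow-up contact leads to any stated action.

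**Working it through.** **Inputs.** From the documents: removal at a CGI-I change of 8 or more (Withdrawal Criteria, both phases); consultation at a CGI-I score of 6 or more (LFMS procedures, both phases); the CGI-I and LFMS rows of the two schedule tables. Not in the documents: the CGI-I scoring range. It is treated as an assumption and varied. The plan gives no derivation of the 8, so there is no figure to reproduce.

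**Step 1: change between two CGI-I ratings.** On a scale of *k* consecutive integer scores the largest change is *k* − 1. A change of 8 needs *k* − 1 ≥ 8, so *k* ≥ 9.

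| Assumed range | Levels *k* | Largest change | Ordered score pairs differing by 8 or more | Score of 6 reachable |
|---|---|---|---|---|
| 1-7 | 7 | 6 | 0 of 49 | yes |
| 0-7 | 8 | 7 | 0 of 64 | yes |
| 1-8 | 8 | 7 | 0 of 64 | yes |
| 0-8 or 1-9 | 9 | 8 | 2 of 81 | yes |
| 1-10 | 10 | 9 | 6 of 100 | yes |
| 0-10 | 11 | 10 | 12 of 121 | yes |

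On the three shorter forms the criterion cannot be met from any starting score. On nine levels it is met only by a move from one end of the scale to the other.

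**Step 2: other readings of the word change.**

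- CGI-I against CGI-B, both assumed 1-7: 7 − 1 = 6.
- CGI-I assumed 1-7 against a CGI-B that starts at 0: 7 − 0 = 7.
- The CGI-I score itself taken as the change, on 1-7: at most 7.

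All three are below 8.

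**Step 3: the two rules together.** On an assumed 1-7 form with 4 meaning no change, a score of 6 is 6 − 4 = 2 points worse than no change, and the top score is 7 − 4 = 3 points worse. The consultation rule can be met; the removal rule cannot.

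**Step 4: coverage of the score-of-6 check.**

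- Phase 1: the CGI-I is marked at Visits 2-9, which is 8 contacts = 6 LFMS visits + 2 follow-up visits (5 and 9). LFMS visits without the check: 6 − 6 = 0. One of the 2 follow-up visits (Visit 5) precedes further LFMS, and the check is made again at Visit 6.
- Phase 2: the CGI-I is marked at Visits 3-8 and two calls, which is 8 contacts = 5 LFMS visits + 3 follow-up contacts. LFMS visits without the check: 5 − 5 = 0. None of the 3 follow-up contacts precedes further LFMS.

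**The case against.** The strongest objection is that the scoring range is nowhere in the documents. They show only that a score of 6 is possible. On a form of nine or more levels the criterion can be met. This stands, and it is why unreachability is stated here only as conditional. The absence of a named reference rating does not depend on the range.

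It can also be said that baseline is the natural reference: one CGI rating carries that name, and the CGI-I starts at the next visit. That is a reasonable reading, but the criterion does not state it, and on the forms assumed above it still gives at most 6 or 7.

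A reader might infer that the two thresholds contradict each other. The documents do not support that. A discretionary step at a score of 6, followed by mandatory removal at a larger change, is coherent. The difficulty is that on a short form the second step would never be taken.

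A reader might also infer that subjects could be exposed to LFMS with no working CGI-I safeguard. The documents do not support that either. Every LFMS visit has the score-of-6 check before exposure. Staff may end participation at any time, and the Safety monitoring section lets the principal investigator withdraw a subject after an event.

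On follow-up, the score-of-6 rule could be taken to travel with the CGI-I wherever the Safety Measures are given. The follow-up text restates only the C-SSRS action, so this should be made explicit. The gap is small. Four of the five follow-up contacts come after the last exposure, and the C-SSRS, MADRS item 10 and adverse-event check-ins still apply. The Phase 2 follow-up contacts also repeat the HARS and YMRS, though without an action threshold for general worsening.

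**Conclusion.** The threshold is wrong as written, conditional on the assumed range. Without any assumption, the criterion names no reference rating and needs at least nine levels. On an assumed 1-7 form (largest change 6), or on 0-7 or 1-8 (largest change 7), it can never be met, and the tier above the score-of-6 consultation rule would not operate. If the form in use has nine or more levels, printing its range settles that part; the missing reference rating remains.

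The consequence is minor. No LFMS visit in either phase lacks the score-of-6 check. The follow-up contacts without a restated CGI-I action are 2 of 8 CGI-I contacts in Phase 1 and 3 of 8 in Phase 2. It would go too far to infer that the tolerability endpoint or any efficacy analysis is compromised: nothing in the documents makes either depend on this criterion.

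**What to change.** In the Withdrawal Criteria of both phases, replace the change-of-8 clause with: a CGI-I score of 6 or more prompts study-physician consultation, and the subject is removed unless the physician documents that continuing is safe. This keeps the existing threshold and makes removal the default, so the entry is firmer than a purely discretionary step in a list of objective criteria.

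Alternatively, the study physicians may set another threshold within the range of the form, with that range printed in the protocol. If a change rule is kept, name the reference rating, such as the CGI-B, and say that worsening is meant.

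State the same trigger for every contact where the CGI-I is already given, including Phase 1 Visits 5 and 9, Phase 2 Visit 8 and the two Phase 2 phone calls.

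The change is protocol wording only and adds no assessments. Its downside is a few more physician consultations.

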During the screening visit, a trained clinical study staff member will interview and assess the subject using the Screening Measures, during which a detailed medical history will be obtained and current medications noted. Suicidality risk is assessed as part of the Safety Measures; a positive response to items 4 or 5 of the C-SSRS will prompt the use of the Suicidality SOP.

A urine drug screen and, if female, a pregnancy test will be performed. Subjects will be accepted for the treatment trial based on the interview and review of results by a study physician.

The screening visit, including the rating scales and physical exam, will take approximately 2 hours and will be done up to one week before the baseline visit. If subjects meet study criteria after the screening visit, a baseline visit will be scheduled.

Baseline (Visit 2) Procedures

Contingent on a successful screening visit, subjects will come in for a baseline visit on the Thursday or Friday prior to the 5 days of consecutive LFMS treatment. This visit will take about 1 hour to complete. Subjects will be administered Long- and Short-Term mood scales as well as the Safety Measures. A positive response to items 4 or 5 on the C-SSRS will prompt the use of the Suicidality SOP (see ‘Suicidality Procedures’ above).

LFMS (Visits 3-7) Procedures

Subjects will come in for 5 daily consecutive LFMS treatments over a period of five days, Monday-Friday. If subjects are unable to come in for five consecutive days due to a scheduling conflict, we will accept a schedule of four consecutive days without considering this a protocol deviation. Women of childbearing potential will be required to complete a urine pregnancy screen at screening and before each LFMS procedure.

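### The Suicidality Procedures section requires C-SSRS questions 4 and 5 to start the SOP; every visit and phone-call section requires 4 or 5

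*Combined protocol and SAP*

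**What the plan says.** In the Phase 2 protocol, section V, Safety Procedures, item h (Suicidality Procedures), the trigger list reads: "The following mood rating items and thresholds trigger use of the Suicidality SOP: C-SSRS, “yes” to questions 4 and 5". The same list continues with "MINI, “yes” on items B7, B9 or B10" and a MADRS item 10 threshold. The bullet before it describes the SOP itself, which "uses the responses to questions 4 and 5 as a threshold for physician involvement". It adds: "If the responses to these two questions are “yes” then the study physician will be contacted".

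The Phase 2 contact sections state a different C-SSRS rule for the same SOP:

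- Screening (Visit 1): "a positive response to items 4 or 5 of the C-SSRS will prompt the use of the Suicidality SOP".
- Baseline (Visit 2): "A positive response to items 4 or 5 on the C-SSRS will prompt the use of the Suicidality SOP".
- LFMS (Visits 3-7) and Follow-up Visit (Visit 8): "any positive response to items 4 or 5 will prompt the use of the Suicidality SOP".
- Follow-up Phone Calls: "a positive response to question 4 or 5 on the C-SSRS will trigger the Suicidality SOP".

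The Baseline, LFMS and Visit 8 statements each refer the reader back to Suicidality Procedures. Phase 1 follows the same pattern: *and* in its Suicidality Procedures (section V, Safety Procedures, item a), and *or* in its Screening, LFMS and Follow-up sections. The last two of these carry the same cross-reference.

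**The concern.** The C-SSRS is the one listed trigger instrument scheduled at all 10 Phase 2 contacts, so its threshold needs a single meaning. As written, staff who follow the cross-reference from a visit section arrive at a narrower rule than the one they left. A subject who answers yes to exactly one of the two questions could be handled differently depending on which section is followed.

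There are two layers. The first is entry to the SOP. The second is physician contact once the SOP is open, which is also described in terms of both answers being yes. Correcting the entry rule alone would leave the second layer unresolved.

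**Working it through.** The plan has no figure to reproduce here. The check compares the rules by response pattern, then counts where each rule is stated.

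**1. Does *and* mean both?** It could be loose wording for either. Two features of the same section point the other way. The trigger list writes *or* for the MINI items ("MINI, “yes” on items B7, B9 or B10") and between the MADRS scores. The preceding bullet makes physician contact depend on the two questions being yes. Both items is the natural reading.

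**2. The rules by response pattern**

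| Q4 | Q5 | SOP entry, trigger list (*and*) | SOP entry, visit and call sections (*or*) | Physician threshold as described |
|---|---|---|---|---|
| yes | yes | yes | yes | met |
| yes | no | no | yes | not met |
| no | yes | no | yes | not met |
| no | no | no | no | not met |

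The entry rules disagree in 2 of 4 patterns. In those two, a subject who enters under the visit text still falls short of the stated physician threshold. The text does not forbid a physician call there; it does not state one.

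**3. Statements of the SOP entry rule**

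- *And*: Phase 1 Suicidality Procedures (1) + Phase 2 Suicidality Procedures (1) = 2.
- *Or*, Phase 1: Screening (1) + LFMS visits (1) + Follow-up visits (1) = 3.
- *Or*, Phase 2: Screening (1) + Baseline (1) + LFMS visits (1) + Visit 8 (1) + phone calls (1) = 5.
- *Or*, total: 3 + 5 = 8.
- *Or* with a cross-reference to Suicidality Procedures: Phase 1 LFMS and Follow-up (2) + Phase 2 Baseline, LFMS and Visit 8 (3) = 5 of 8.

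**4. Contacts covered**

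- *Or* rule, Phase 2: Visit 1 (1) + Visit 2 (1) + Visits 3-7 (5) + Visit 8 (1) + two calls (2) = 10 of 10.
- *Or* rule, Phase 1: Visit 1 (1) + Visits 2-4 and 6-8 (6) + Visits 5 and 9 (2) = 9 of 9.
- *Or* rule that points to the *and* section, Phase 2: 1 + 5 + 1 = 7 of 10 (Visits 2-8).
- *Or* rule that points to the *and* section, Phase 1: 6 + 2 = 8 of 9 (Visits 2-9).

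**5. Other Phase 2 routes, by contact**

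- Spontaneous report: 10 of 10, but it depends on the subject raising it.
- MADRS item 10: 8 of 10. The MADRS is not given at Visits 4 and 6, so the C-SSRS is the only scheduled scale among the listed triggers at those two treatment visits.
- MINI: 1 of 10 (Visit 1).
- Stated physician review of results: 1 of 10 (Visit 1).

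The first three routes lead into the SOP. As the protocol describes it, the SOP then applies the same two-question threshold before physician contact.

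**The case against.** The two texts can be followed together. The trigger list never says it is exhaustive, and the *or* rule is written at every contact. Staff who apply both would open the SOP on either item. The cross-reference can be read as pointing to what the SOP does, not as replacing the trigger just stated. This argument stands for SOP entry: one yes already has a written instruction at all 10 Phase 2 contacts. It does not reach physician contact, which is described only in Suicidality Procedures and only for both answers being yes.

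The physician threshold is the protocol's summary of the GPMADOC SOP, a separate document not included with the protocol. The SOP may already act on either item. That is a real limit: the conflict in wording is certain, but a difference in actual handling is not.

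Other protection exists. The Withdrawal Criteria use the C-SSRS and a study clinician's opinion at any time, with no both-items condition. The psychosocial risk text in section VII calls for an immediate call to a study physician and the subject's own clinician. That call is conditioned on an increase in suicidal thinking. Since dangerous or active ideation is excluded at entry, a new yes after screening would plausibly count as an increase, but the protocol does not say so.

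Finally, the Phase 1 statements largely duplicate those in Phase 2. If Phase 1 text is no longer in use, the relevant count is 1 against 5. The conflict is the same.

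**Conclusion.** The concern holds and should be fixed. The protocol gives two thresholds for one patient-safety procedure: *and* in 2 statements, *or* in 8 (1 against 5 in Phase 2 alone). The section staff are sent to for detail holds the narrower one. The more consequential part is the second layer, where a subject positive on exactly one item can enter the SOP without meeting the described threshold for calling the physician. The remaining safeguards reduce this gap but do not close it.

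The conclusion rests on reading *and* as both, which the wording of the same section supports, and on the protocol's description of the SOP being accurate. How many subjects would be positive on exactly one item cannot be estimated from the documents. No endpoint, analysis, sample size or removal criterion is affected.

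**What to change.** 1. Compare the protocol with the GPMADOC SOP document, so that the two agree after the change.
2. In Phase 2, section V, item h, change the C-SSRS entry in the trigger list to a yes on question 4 or 5. In the preceding bullet, state that a yes to either question leads to physician contact.
3. Make the same two changes in Phase 1, section V, Safety Procedures, item a, if that text is still in use.
4. If the SOP itself requires both answers before physician contact, amend the SOP and the protocol together.

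This brings the safety section into line with all eight visit and contact statements. The cost is a wording change in one section (two if Phase 1 text is live), a check against the SOP and, if step 4 applies, an SOP amendment. No new assessments or staff are needed. The downside is possibly a few more physician contacts, for subjects positive on exactly one item.
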